Secondary hypotheses include that solriamfetol treatment at maximal patient specific dosing will result in improvements in patient-reported excessive daytime sleepiness and sleep quality (e.g. ESS and PSQI), neurocognitive function (see below for neurocognitive battery), fatigue and mood (e.g. Brief Fatigue Inventory, Cancer Fatigue Scale, Beck Depression Inventory), and quality of life (FACT-Brain).

3. Exploratory Hypotheses

Improvements in objective measures of sleep (e.g. actigraphy, sleep diary) will be similar to those reported in prior studies (e.g. obstructive sleep apnea, narcolepsy). We hypothesize that improvements in sleep, neurocognition, fatigue, mood, and quality of life may vary by clinical factors such as corticosteroid use, antiepileptic use, and tumor grade by World Health Organization (WHO) classification.

3 Objectives

1. Primary Objective(s)

1. To estimate the safety of solriamfetol at 75 mg daily, 150 mg daily, 300 mg daily as assessed by NCI CTC Adverse Events (v5.0) in patients with primary gliomas compared to prior studies⁴⁵⁻⁴⁷

2. Secondary Objective(s)

1. To estimate the effect of solriamfetol on sleep by Epworth Sleepiness Scores (ESS) scores in patients with primary gliomas and compare the effect to previously published scores in patients with OSA
2. To estimate the effect of solriamfetol on sleep quality by Pittsburgh Sleep Quality Index scores
3. To estimate the effect of solriamfetol on neurocognitive function based on a disease-specific neurocognitive battery (see neurocognitive battery below)
4. To estimate the effect of solriamfetol on patient-reported fatigue (Brief Fatigue Inventory, Cancer Fatigue Scale) & mood (Beck's Depression Inventory)
5. To estimate the effect of solriamfetol on patient-reported QOL (FACT-Br)
6. To estimate the effect of solriamfetol on objective sleep-wake times by actigraphy and sleep diary (pre- vs post-treatment)

3. Exploratory Objective(s)

1. To explore a biologic gradient effect of increasing doses of solriamfetol on actigraphy
2. To explore differences in clinical activity of solriamfetol by corticosteroid use, antiepileptic use, and tumor grade

4 Patient Selection

Inclusion and exclusion criteria represent standard criteria for other sleep studies in this population (e.g. inclusion criteria) and standard exclusions for prior studies of this agent (e.g. exclusion criteria).^{8,39,40}

1. Inclusion Criteria

1. WHO Grade 2-4 infiltrating glioma by histologic confirmation

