This is a single-arm, open label, non-randomized safety study in patients with glioma with each patient undergoing both a dose-escalation and fixed drug continuation phase of the study. The primary objective is to compare the safety of oral solriamfetol at doses of 75 mg daily, 150 mg daily and 300 mg daily. Secondary objectives include determining the effect of solriamfetol on patient-reported sleep, neurocognition, fatigue, mood, quality of life, and objective measures of sleep.

1. Primary Outcome

1. The primary outcome measure will be adverse events as assessed by the NCI Common Terminology Criteria for Adverse Events (CTCAE) version 5.0.

2. Secondary Outcomes

1. The effect of solriamfetol on patient-reported sleep will be assessed by Epworth Sleepiness Scale (ESS) scores
2. The effect of solriamfetol on patient-reported sleep quality will be assessed by Pittsburgh Sleep Quality Index (PSQI) scores.
3. The effect of solriamfetol on neurocognitive function will be assessed by a disease-specific Neurocognitive Battery (Section 7.8).
4. The effect of solriamfetol on patient-reported associated symptoms will be assessed by the Brief Fatigue Inventory (BFI) and the Cancer Fatigue Scale (CFS) for determining the effect on fatigue and by the Beck's Depression Inventory (BDI) for determining the effect on depression and mood.
5. The effect of solriamfetol on patient-reported QOL will be assessed by the FACT-Brain module (FACT-Br).
6. The effect of solriamfetol on changes in objective sleep-wake times will be assessed by actigraphy and patient-reported sleep diary (see Section 7.8).

3. Exploratory Outcomes

1. Actigraphy in relation to increasing doses of solriamfetol.
2. Differences in clinical activity of solriamfetol by treatment factors will be assessed by recording corticosteroid dose at baseline, antiepileptic use (presence/absence of prescribed antiepileptic and dose at baseline), and tumor grade by World Health Organization (WHO) criteria.

7 Treatment Plan

1. Overview of Treatment Plan

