This is a single-arm, open label, two-part safety study of solriamfetol in patients with WHO grade 2-4 gliomas. Patients with stable disease by clinical examination and neuroimaging who have an ESS \geq 10 and meet all inclusion/exclusion criteria will be recruited and enrolled. First, all patients will receive solriamfetol at escalating doses. Second, all patients will complete a fixed dose drug continuation treatment at the patient-specific maximum tolerated dose.

The study will occur in 3 phases:

Open Label Safety Study of Solriamfetol to Promote Wakefulness and Improve Cognition and Quality of Life in
Patients with Primary Gliomas
Wake Forest Baptist Comprehensive Cancer Center
WFBCCC 98418

1. Pre-Treatment Baseline (~1 week)
2. Flexible Dose Titration (~3 weeks)
3. Fixed Dose Drug Continuation (~6 weeks)

Patients will initially complete a 1-week baseline actigraphy and sleep diary prior to treatment initiation to establish a baseline sleep pattern.

Solriamfetol will be dosed by flexible dose titration starting at 75 mg daily in all patients and escalating after 7 days (1 week) to 150 mg daily and then after 7 days to 300 mg daily for a total duration of 3 weeks (flexible dose titration period). Patients who experience a dose-limiting toxicity will be de-escalated to the last tolerated dose level and move to the fixed dose drug continuation phase. Prior studies incorporating this design have used a 3-day treatment prior to escalation.⁴⁹ For this study, 7 days has been selected to provide a sufficient period of time to observe both immediate and delayed toxicities that could be seen in this population.

Following completion of the flexible dose titration, patients will continue solriamfetol at 300 mg daily or their maximally tolerated dose for a treatment duration of 6 weeks. For this period of the study, 8 weeks has been selected to allow for time to observe both short term improvement in patient-reported sleep as well as potentially more delayed changes in other study endpoints (i.e. fatigue, mood, neurocognition).

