Based on our prior cross-sectional study, we anticipate 30% of patients to be enrolled during adjuvant therapy (i.e. receiving oral chemotherapy), 30% during post-adjuvant surveillance (i.e. not receiving any prescribed antitumor therapy), and approximately 30% during post-recurrent disease treatment (i.e. undergoing salvage treatment with chemotherapy). This will allow for comparisons of toxicity, tolerability, and activity by timing during cancer care.

We anticipate that approximately 20-30% of patients will be taking active corticosteroids and 60% of patients will be prescribed an antiepileptic agent. This will allow us to explore differences in tolerability and activity by these important treatment parameters.

Screening assessments may be completed by telehealth visit. These will be done through MWH when able. If not able, Doximity will be used which is what is done clinically for these patients.

4. Pre-Treatment Baseline

All patients who complete written informed consent and meet eligibility criteria will be registered and will proceed with study treatment. For patients who complete consent at the time of a regularly scheduled visit they can be provided with a baseline sleep diary and actigraph device to complete the Pre-Treatment sleep diary and actigraphy prior to Visit 1 (V1). For patients who elect to take consider study enrollment and return at a later date, sleep diary and actigraphy can be completed after (in the first 7 days after) Visit 1 (V1).

Enrolled patients will complete the pre-treatment study assessments (Section 6.7). Patients will be instructed to complete a 1-week pre-treatment baseline assessment with 7-day sleep diary that records time in bed, time awake, and estimated hours of sleep among other items (Appendix Q) as well as 7-day actigraphy (see Section 7.8.2).

Patients will either return to clinic or receive a telephone call from the study nurse, study coordinator, or study team at the end of this pre-treatment baseline week (Day 7+1 day) to record the completion of pre-treatment baseline actigraphy and sleep diary.

Baseline visit will be performed in-person.

5. Flexible Dosing Titration

Upon completion of pre-treatment baseline assessments, patients will begin flexible dosing titration. All patients will begin solriamfetol 75 mg p.o. once daily. The dose will be titrated every

7 days (+1 day) to 150 mg daily and then 300 mg daily unless the patient experiences symptomatic dose-limiting toxicity.

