The ESS is an 8-item validated instrument (min score 0 – max score 24, Appendix H) that is easy to implement and an accepted screening tool for symptoms of excessive daytime sleepiness. It has been well studied in patients with EDS and brain tumors.^{7,13,45-47,51,52} An accepted cutoff of ESS^{>10} has been used to indicate EDS for enrollment into studies evaluating therapeutic interventions.⁵⁰ Prior studies have indicated that a 25% reduction in ESS may be useful as a threshold to identify patients who respond to solriamfetol treatment.⁵³

The PSQI is a 19-item validated self-report questionnaire (Appendix I) assessing sleep quality including subjective sleep quality, sleep latency, sleep duration, sleep efficiency,

and daytime dysfunction. Prior studies demonstrate impaired sleep quality in patients with cancer⁴⁰ and brain tumors.⁵²

The ESS and PSQI measure non-overlapping orthogonal dimensions of self-reported sleep-wake symptoms.⁵²

These measures will be completed prior to flexible dose titration, at the interim time point after flexible dose titration and before fixed dose continuation, and at end of treatment (see 7.2 Study-Related Activities).

2. Objective measures of sleep activity:

Actigraphy and sleep diaries are widely used, efficient, and affordable methods for measuring sleep-wake time.

Actigraphy has been shown to provide accurate data that is comparable to polysomnography⁵² and is increasingly used to provide an objective measure of sleep in clinical trials.⁵² Actigraph devices are worn on the wrist and record movements that can be used to estimate sleep patterns using specialized computer software programs. Completion of actigraphy will be recorded (Appendix R).

A 7-day sleep diary (Appendix R) will be provided to all patients at the time of consent and/or study enrollment. All sleep diaries will be collected over 7-days (i.e. 7-day sleep diary and 7-day actigraphy) including at pre-study baseline, throughout each dose of the dose escalation phase, and during the first 7-days and last 7-days of the fixed dose drug continuation phase of the study. Caregivers may complete sleep diaries for patients. Actigraphy will be collected continuously from baseline to end of treatment (see 7.2 Study-Related Activities).

3. Neurocognitive Battery:

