3. Analysis of Exploratory Objective

13.3.1 To explore the dose response effect of solriamfetol on actigraphy, linear regression models will be used where the dosage will be treated as an ordinal variable.

Transformation of actigraphy will be performed to satisfy the normality assumption if needed.

13.3.2 The analysis will be the same as that specified in 13.1.

4. Power and Sample Size

We plan to recruit around 36 participants.

In the prior phase 2a and phase 2b studies in patients with narcolepsy which had similar sample sizes, no patients in the phase 2a and three patients in the phase 2b study required discontinuation of study medication, though two of these discontinuations were not attributed to the study drug.^{46,47} In the prior phase 3 study, 9 patients (9%) including one in the 75 mg arm, 3 in the 150 mg arm, and 5 in the 300 mg arm required discontinuation due to treatment related AEs.⁴⁵ In the current study, 36 patients will receive 75 mg daily dosing. We conservatively estimate that at least 33 patients will escalate to 150 mg daily, and at least 30 patients will escalate to receive 300 mg daily. These estimates are felt to be overly conservative based on data from these prior studies in patients narcolepsy.

From prior studies, the most common adverse event proportions range from 10% to 20%. Assuming 10% and 20% of adverse event proportion, the detectable proportions for the combined dosage are 24% and 36%, respectively, in order to reach 80% power at a significance level of 0.1 (given the pilot nature of this study) and a two-sided test. These detectable proportions are reasonable. If we observe an adverse event proportion in the patients with primary gliomas that is higher than 36%, then the adverse event proportion is significantly higher than the other study populations. In practice, if an adverse event proportion is higher than 50%, then the safety/tolerability of solriamfetol needs to be questioned. We should have enough power for this primary analysis. Note that this study allows us to determine safety profiles for the 3 doses of solriamfetol. It is primarily for descriptive purpose and to generate data on safety and estimation of effect size for the design of a subsequent randomized study powered to determine drug activity. The results generated from this study will be beneficial for the future research study.

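### The actigraphy dose-response regression in Section 13.3.1 names no time term, although dose and week coincide during titration for patients who escalate on schedule

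*Combined protocol and SAP*

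**What the plan says.** The exploratory objective in Section 3.3 is "To explore a biologic gradient effect of increasing doses of solriamfetol on actigraphy". Its analysis, in Section 13.3.1, is that "linear regression models will be used where the dosage will be treated as an ordinal variable", with a transformation if normality is doubtful. The section says nothing on time, on repeated measurements of one patient, or on which weeks are analysed.

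The dose order is fixed. Section 7.1 has solriamfetol "starting at 75 mg daily in all patients and escalating after 7 days (1 week) to 150 mg daily", with 300 mg in the third week. Section 6 states the design: "This is a single-arm, open label, non-randomized safety study in patients with glioma".

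Three statements qualify this:

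- Section 7.5 titrates "to 150 mg daily and then 300 mg daily unless the patient experiences symptomatic dose-limiting toxicity", so not every patient need reach the top dose.
- Section 13.4 expects 36 patients at 75 mg and that "at least 33 patients will escalate to 150 mg daily, and at least 30 patients will escalate to receive 300 mg daily".
- Six weeks at a fixed dose follow titration (Section 7.6). Section 7.8 says "Actigraphy will be collected continuously from baseline to end of treatment", as do Section 7.6 and a footnote in Section 7.2. Section 7.1 instead lists seven-day recordings at each escalation and in the first and last fixed-dose weeks.

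**The concern.** If each dose step is also a step of one week, a slope on dose cannot be told from a slope on time. Sources of drift are plausible. They include getting used to the device and regression to the mean after entry on a sleepiness threshold. Section 7.3 expects about 30% of patients on adjuvant and 30% on salvage chemotherapy, and Section 7.10 allows medically indicated changes in steroid and sedative doses.

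The protocol's own background shows how such a design can mislead. In the phase 2a narcolepsy trial (Section 1.5.1), drug-treated patients took 150 mg in week 1 and 300 mg in week 2, and ESS change went from -5.3 to -6.7, a step of -1.4. Placebo went from -1.2 to -2.4 over the same interval, a step of -1.2. Most of the apparent dose step also occurred without drug. That is one trial, and ESS rather than actigraphy. In the phase 3 narcolepsy trial placebo moved the other way, from -2.7 at week 1 to -1.6 at week 12. The present trial has no placebo arm to reveal either pattern.

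Section 13.4 says the study is to supply effect-size estimates for a later randomized trial. A time trend labelled as dose response could mislead that design.

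**Working it through.** The documents give no power, effect size or SD for actigraphy, so there is no figure to reproduce. The check is on the design.

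**Inputs.** Dose is coded 0 (baseline), 1, 2, 3 and week 0 to 9, from Sections 7.1 and 7.6. There are 36 patients and a two-sided 0.10 level, from Section 13.4; no level is stated for actigraphy. Drift per week is assumed.

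**Titration only, all escalating.** Dose and week are both 1, 2, 3. Their correlation is 1.0, the matrix of intercept, dose and week has rank 2 of 3, and the whole of any linear drift enters the dose slope.

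**Titration with 36/33/30.** Assume 30 patients take 1, 2, 3; three stop after week 1; three take 1, 2, 1. Over these 102 patient-weeks the correlation is 0.915, and the dose slope absorbs 0.92 week of drift per step. If the six patients give no data after they stop escalating, the correlation is again 1.0.

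**False gradient, inert drug, linear drift, independent observations.** The sum of squares of dose is 36 × [(1-2)² + 0 + (3-2)²] = 72, so the slope SE is SD/√72 = 0.118 SD. The expected slope equals the drift. With z = drift/0.118, P(significant) = Φ(z - 1.645) + Φ(-z - 1.645):

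| Drift, SD per week | z | P(significant) |
|---|---|---|
| 0.1 | 0.85 | 0.22 |
| 0.2 | 1.70 | 0.52 |
| 0.3 | 2.55 | 0.82 |

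A simulation with an assumed within-patient correlation of 0.5 gives 13%, 52% and 89% by ordinary regression, and 33%, 76% and 97% by a within-patient test. A patient term alone does not help, because the confounding lies within patients. With no drift, ordinary regression rejects in 2.7% of trials and the within-patient test in 10%.

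**Adding constant-dose weeks.** For weeks 0 to 9, dose is 0, 1, 2, then 3 seven times. The sums of squares and products are Sdd = 10.4, Sdw = 23.0 and Sww = 82.5. So r = 23.0/√(10.4 × 82.5) = 0.785 and VIF = 1/(1 - r²) = 2.61. With both terms fitted, the dose SE is SD × √[2.61/(36 × 10.4)] = 0.083 SD under independence. Without a week term, the dose slope absorbs 23.0/10.4 = 2.2 weeks of drift per step. Other choices of weeks, with all 36 escalating:

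| Weeks entered | r | VIF | Drift absorbed per step if no week term | Dose SE with week term |
|---|---|---|---|---|
| 1-3 | 1.00 | infinite | 1.0 | not estimable |
| 1-4 and 9 | 0.66 | 1.8 | 2.3 | 0.125 SD |
| 0-4 and 9 | 0.74 | 2.2 | 1.9 | 0.088 SD |
| 1-9 | 0.71 | 2.0 | 2.75 | 0.118 SD |
| 0-9 | 0.79 | 2.6 | 2.2 | 0.083 SD |

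The rows with weeks 4 and 9 only match the recording windows in Section 7.1; those with every fixed-dose week match Section 7.8. Both terms can be estimated either way.

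**Does a linear week term cure it?** Assume an inert drug and a drift that levels off, 0.5 × (1 - e^(-week/τ)) SD, with τ of 1, 2 or 3 weeks. Least squares on this curve gives the expected dose coefficients below; each is divided by its SE and put through the formula above.

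| Model | Coefficient, SD per step (τ = 1, 2, 3) | P(significant) |
|---|---|---|
| Dose + linear week, weeks 0-9 | 0.150, 0.117, 0.086 | 0.56, 0.41, 0.27 |
| Dose + linear week, weeks 1-9 | 0.079, 0.090, 0.073 | 0.17, 0.20, 0.16 |
| Dose only, weeks 1-3 | 0.080, 0.096, 0.087 | 0.18, 0.21, 0.19 |

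Under early drift, the linear-week model that includes baseline does worse than the titration-only regression.

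**The case against.** The analysis is exploratory, Section 13.4 calls the study mainly descriptive, and no decision rests on this slope. That stands, and it fixes the severity.

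The drift sizes have no source in the documents, and at 0.1 SD per week the excess over the nominal 10% is modest. That stands too. The percentages show sensitivity to an assumption and do not forecast this trial.

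A reader might infer that every patient takes all three doses and that dose and week are one variable throughout. The documents do not support this: escalation stops for dose-limiting toxicity, the plan allows for 36/33/30, and the fixed-dose weeks separate the two. A reader might also infer that the plan has decided to ignore the fixed-phase recordings or to treat repeated observations as independent. Section 13.3.1 is silent on both. Nor does Section 3.3 assert a gradient; it sets out to explore one.

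The strongest objection is to the obvious remedy. Habituation and regression to the mean tend to come early, and a linear week term estimated mainly from flat later weeks leaves them in the dose estimate. The last table bears this out, so the adjusted model must be presented with its assumption and cannot be offered as a cure.

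**Conclusion.** The concern holds in limited form. As written, Section 13.3.1 cannot separate dose from time in the titration weeks of patients who escalate on schedule, and it specifies nothing that would separate them elsewhere. Entering the fixed-dose weeks without a time term does not help, since about 1.9 to 2.75 weeks of drift then load on each dose step if all patients escalate.

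For linear drift of 0.1 to 0.3 SD per week, an inert drug would show a significant slope in about 22% to 82% of trials. This assumes independent observations, 36 patients at each dose and a two-sided 0.10 level. Drift against the direction of benefit would instead mask or reverse a real gradient. The consequence is confined to what the actigraphy objective in Section 3.3 can conclude; the safety and ESS analyses are untouched.

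**What to change.** In Section 13.3.1:

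1. Name the actigraphy weeks analysed, and reconcile Section 7.1 with Sections 7.2, 7.6 and 7.8 on when actigraphy is recorded.
2. Replace the ordinary regression with a repeated-measures model on weekly summaries, with a patient-level term.
3. Describe any result from titration weeks alone as a dose/time trend, not as a dose response or biologic gradient.
4. Add an analysis with both dose and week that includes the constant-dose weeks (VIF about 1.8 to 2.6 under either recording schedule). State that it assumes the same time trend in titration and in the fixed phase.
5. Check that analysis with a levelling-off time term and without the baseline week. A levelling-off curve resembles a dose code that rises and then stays flat, so this check will be imprecise; the report should say so.

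The cost is some SAP wording, slightly more analysis of data already collected, and a weaker claim for an exploratory objective. Under independence, the dose SE over weeks 0 to 9 with a week term (0.083 SD) is below that of the three-dose regression (0.118 SD). Without baseline it is about the same with every fixed-dose week (0.118 SD), and slightly larger with only the first and last (0.125 SD).

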The main study assessments will be performed at baseline prior to flexible dose titration and then at the end of the fixed dose drug continuation phase. This will include: (1) patient reported measures, (2) objective measures of sleep activity, (3) neurocognitive functioning (4) assessment of associated symptoms such as fatigue, mood, and (5) quality of life. Additional assessment of patient-reported measures will be performed after dose escalation and prior to the fixed dose drug continuation. Due to practice effects and other issues related to repeated measurement, neurocognitive data will only be collected pre- and post-treatment.

Sleep diaries will be completed continuously throughout the ~10 week study. Seven-day actigraphy will be completed at each dose escalation and during the first and last weeks of fixed dose drug continuation.

Additional assessments will be performed as per the standard of care. In this population, it is standard of care for MR Brain to be performed roughly every 8-16 weeks. Data on tumor status by imaging (e.g. stable disease, imaging progression, etc) will be recorded prior to study treatment and following study treatment to assess for tumor progression as a factor contributing to changes in patient-reported and clinician assessed outcome measures.

Adverse events will be assessed every 7 days during flexible dose titration (via telephone) and at the end of the fixed dose treatment. Adverse event data will be compared to that reported in patients with narcolepsy.⁵⁰

Open Label Safety Study of Solriamfetol to Promote Wakefulness and Improve Cognition and Quality of Life in
 Patients with Primary Gliomas
 Wake Forest Baptist Comprehensive Cancer Center
 WFBCCC 98418

2. Study-Related Activities

	Pre-Study ^a ^k	Baseline Visit V1 (D1)	Begin Flexible Dose Titration (D8+1 dy)	Flexible Dose D7 (D15+1 dy)	Flexible Dose D14 (D22+1 dy)	Fixed Dose Initiation Visit V2 ^k (D29+7 dys)	End of Treatment Visit V3 (D70+7 dys)	30 day Follow Up Visit V4 ^k
Informed consent	X							
Demographics	X							
Medical history	X							
Concurrent meds	X					X	X	
Physical exam ¹		X				X	X	X
Vital signs ^b	X ^c	X				X	X	X
CBC w/diff, platelets	X					X	X	X
Serum chemistry ^d	X					X	X	X
B-HCG ^e	X							
Electrocardiogram (EKG)		X				X		
Adverse event evaluation		X	X ^f	X ^f	X ^f	X	X	X
Epworth Sleepiness Scale (ESS)	X	X ^g	X ^g	X ^g	X ^g	X ^g	X ^g	
Sleep Measures: Sleep diary, Actigraphy ^h		X ⁱ	X	X	X	X	X	

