Pittsburgh Sleep Quality Index (PSQI)		X				X	X	
Associated Symptom PROMs: BFI, CFS, BDI		X				X	X	
QOL PROMs: FACT-Br		X				X	X	
Neuro-cognitive Battery		X					X	
Standard of Care MR Brain ^a	X						X ^j	

¹ Patient's undergoing telehealth assessment at the pre-screening timepoint require virtual examination by observation only. Blood draw and laboratory testing can be performed locally and reviewed remotely.

^a Pre-study requirements listed in table must be completed **within** 21 days prior to registration.

^b Blood pressure (mmHg), heart rate (BPM)

^c Height, Weight, M² Patients undergoing telehealth assessment can provide this information verbally using home device (e.g. scale).

^d Albumin, alkaline phosphatase, total bilirubin, bicarbonate, BUN, calcium, chloride, creatinine, glucose, potassium, total protein, SGOT[AST], SGPT[ALT], sodium.

^e Serum pregnancy test (women of childbearing potential).

^f May be performed by telephone.

^g Epworth Sleepiness Scale (ESS) will be completed either in the clinic (D1, D29, D70) at each of the study visits (V1, V2, V3) or by telephone (D8, D15, D22) during the flexible dose escalation portion of the study.

^h 7-day sleep diary is to be completed at baseline (D1-7), continuously during dose escalation (D8-14, D15-21, D22-28), and during the first and last week of fixed dose drug continuation (~D29-35 and ~D63-70). Actigraphy will be collected continuously.

ⁱ Patients may complete the baseline sleep diary and actigraphy prior to the Baseline Visit (V1) or after the Baseline Visit (V1).

^j Post-treatment MR Brain is to be performed D85 \pm 42 days.

^k Study visits may be conducted via telehealth visit. Blood draw and EKG (when appropriate) can be performed locally and reviewed remotely.

3. Screening

Glioma patients seen at the Wake Forest Baptist Medical Center will be considered for eligibility at or before their scheduled visits. In general, patients may be approached at the time of routine outpatient visit for follow up with neuro-oncology, medical oncology, radiation oncology, and neurosurgery.

Patients who are identified as potential study candidates will have an opportunity to hear about the study and complete written informed consent. Patients who sign informed consent and do not meet eligibility criteria will be considered screen failures, will not be evaluable for the primary endpoint, will not count toward the total sample size, and this enrollment will be replaced.

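### Section 13.3.2 sends the clinical-activity-by-subgroup objective to the adverse-event analysis in 13.1, and 13.3.1 does not say how repeated actigraphy from the same patient is handled

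*Combined protocol and SAP*

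**What the plan says.** Section 3.3 lists two exploratory objectives: "To explore a biologic gradient effect of increasing doses of solriamfetol on actigraphy" and "To explore differences in clinical activity of solriamfetol by corticosteroid use, antiepileptic use, and tumor grade". Section 2.3 shows what activity covers: "We hypothesize that improvements in sleep, neurocognition, fatigue, mood, and quality of life may vary by clinical factors such as corticosteroid use", with antiepileptic use and WHO grade as the other factors. Section 6.3 repeats the second objective as an outcome: "Differences in clinical activity of solriamfetol by treatment factors will be assessed by recording corticosteroid dose at baseline", along with antiepileptic use and dose at baseline, and grade. Section 7.3 gives the expected shares (20-30% on corticosteroids, 60% on an antiepileptic) and adds "This will allow us to explore differences in tolerability and activity by these important treatment parameters".

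The analysis text for objective 2 is one sentence: "13.3.2 The analysis will be the same as that specified in 13.1". For objective 1, section 13.3.1 names linear regression with dose as an ordinal variable, and a transformation if normality requires it.

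On actigraphy collection, section 7.1 says "Seven-day actigraphy will be completed at each dose escalation and during the first and last weeks of fixed dose drug continuation", whereas footnote h of the schedule in 7.2 says "Actigraphy will be collected continuously". Sections 7.6 and 7.8 also describe continuous collection.

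**The concern.** An analyst who follows 13.3.2 literally produces adverse-event tables by dose and nothing about activity in any subgroup. The endpoint, the coding of each factor and the contrast would then be chosen with the data in view. With few corticosteroid users expected, those choices could decide the result. Section 13.5 says the pilot data should inform development in patients on antiepileptics or corticosteroids, so these comparisons are likely to be read.

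In 13.3.1 the dose comparison is largely within patients, because everyone starts at 75 mg and most go on to 150 and 300 mg. Regression that ignores this does not use the right variance for the dose slope. Neither the actigraphy variable nor its unit (night or week) is named, so one cannot tell whether a true gradient would be missed or a false one declared.

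**Working it through.** **13.3.2: could any analysis section answer the objective?**

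| Section | Outcome | Contrast | Compares activity between corticosteroid, antiepileptic or grade groups? |
|---|---|---|---|
| 13.1 | CTCAE events | Three doses, chi-squared or Fisher; grade 3+ proportions with 95% CI | No |
| 13.2 | Secondary scores | Pre against post; ESS change against a published OSA value | No |
| 13.3.1 | Actigraphy | Trend over dose | No |

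Reading the cross-reference as a slip for 13.2 or 13.3.1 does not supply the contrast.

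Expected group sizes from 7.3 and N = 36: corticosteroids 0.20 × 36 = 7.2 to 0.30 × 36 = 10.8, so about 7 to 11; antiepileptics 0.60 × 36 = 21.6, so about 22 against 14. A two-sample t-test at two-sided 0.10 with 80% power, if all 36 contribute, detects 1.07 to 0.92 SD of change for corticosteroids (7 vs 29 to 11 vs 25) and 0.87 SD for antiepileptics. A properly specified comparison would still give wide intervals.

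**13.3.1: what plain regression would do.** The plan gives no figure to reproduce.

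Inputs from 13.4: 36/33/30 patients at 75/150/300 mg; two-sided level 0.10 (13.3 states none). Assumed: correlations, variance shares, total variance 1, and dropout in order, so that 30 patients have three doses, 3 have two and 3 have one.

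*One weekly value per dose, dose coded x = 1, 2, 3:*

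- N = 99; mean x = (36 + 66 + 90)/99 = 1.9394; w = x − mean.
- Sxx = 36(0.9394)² + 33(0.0606)² + 30(1.0606)² = 65.636.
- Squared patient sums of w: 30(0.1818)² + 3(0.8788)² + 3(0.9394)² = 5.956.
- Under equal correlation ρ, Q = (1 − ρ)·65.636 + ρ·5.956, and the true SE of the fitted slope is √Q/Sxx.
- Expected residual variance: s² = [99 − T/99 − Q/Sxx]/97, with T = (1 − ρ)·99 + ρ·285 and 285 = 30·9 + 3·4 + 3·1. Reported SE = √(s²/Sxx).
- At ρ = 0.5: Q = 35.796, true SE = 0.0912; T = 192, s² = 0.995, reported SE = 0.1231; ratio R = 1.351.
- True level = 2[1 − Φ(1.645R)]; at R = 1.351 this is 0.026.
- Power at the slope where a model using the correct correlation has 80%: δ = (1.645 + 0.842)·SE(model). At ρ = 0.5, SE(model) = 0.0889 and δ = 0.221; power = Φ(0.221/0.0912 − 1.645 × 1.351) = 0.58.

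| Weekly values, correlation 0.5 / 0.6 / 0.7 | SE ratio R | True level (nominal 0.10) | Power where a mixed model has 80% |
|---|---|---|---|
| Equal correlation | 1.35 / 1.48 / 1.65 | 0.026 / 0.015 / 0.007 | 58% / 48% / 34% |
| AR(1), three doses | 1.13 / 1.22 / 1.34 | 0.062 / 0.046 / 0.028 | 73% / 67% / 58% |
| AR(1), baseline week added as level 0 | 1.00 / 1.04 / 1.12 | 0.10 / 0.087 / 0.065 | 79% / 76% / 71% |

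*Seven nightly rows per week.* With variance shares p (patient), k (patient-week) and e (night), Sxx = 7 × 65.636 = 459.45 and Q = 49p·5.956 + 49k·65.636 + 7e·65.636. For 0.4/0.1/0.5, Q = 116.7 + 321.6 + 229.7 = 668.1.

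| Shares p / k / e | SE ratio R | True level |
|---|---|---|
| 0.4 / 0.1 / 0.5 | 0.82 | 0.175 |
| 0.4 / 0.2 / 0.4 | 0.69 | 0.255 |
| 0.3 / 0.3 / 0.4 | 0.61 | 0.319 |
| 0.5 / 0 / 0.5 | 1.10 | 0.071 |

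**The case against.** The strongest reply on 13.3.1 is that it is silent on correlation and does not assert independence. A patient effect or clustered errors could be added under the words used. A reader might infer that the plan treats rows as independent and will overstate, or will miss, a dose gradient. The documents support neither. The direction depends on an unstated unit and on correlations they do not give, and one scenario above (AR(1) 0.5 with the baseline week) shows essentially no error. What stands is that the unit and the handling of repeated measures are unspecified.

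On 13.3.2, one can say that 7.3 also mentions tolerability, which 13.1 could be adapted to serve. That is true, but the stated objective and outcome are activity. A reader might also infer that 13.1's proportion tests are meant for ESS responders, since 7.8 says a 25% reduction may be a useful threshold, and then criticise the power of that test. No section makes response an endpoint, so the plan contains no such test to criticise. Any power simulation for it would also have to keep ESS within 0 to 24.

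Finally, section 13.4 describes the study as mainly descriptive, and both analyses are exploratory. That limits the weight of the point. How each factor is coded is the sponsor's choice: 6.3 records doses as well as use, and no grade grouping is given.

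**Conclusion.** The point holds as a minor one, in two parts of different strength. Section 13.3.2 is wrong as written: following it gives no activity contrast for any of the three factors, and no other section supplies one. This rests on the text alone. Section 13.3.1 is under-specified. If it is fitted as plain regression, the standard error is generally wrong: 1.35 to 1.65 times the true value with weekly values and equal correlation 0.5 to 0.7, 1.00 to 1.34 across the AR(1) cases, and 0.82 to 0.61 with nightly rows and a patient-week share of 0.1 to 0.3 (1.10 with no such share). These figures are illustrations under assumed correlations, not properties of the plan. A reader might infer that the safety result or the sample size is undermined; neither uses section 13.3, and both are unaffected.

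**What to change.** Replace 13.3.2 with wording such as: *V1-to-V3 change in ESS (priority) and in the other activity scores (supportive) will be compared by linear regression on baseline score and one factor per model: baseline corticosteroid use, baseline antiepileptic use, WHO grade. Differences will be reported with confidence intervals and labelled exploratory.* Before analysis, the sponsor should choose and state the coding (use or recorded dose; grouping of grade). It should also give the expected subgroup sizes, about 7 to 11 on corticosteroids and 22 on antiepileptics of 36.

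Replace 13.3.1 with a linear mixed model with a random patient intercept, or GEE clustered on patient. The outcome is one named weekly actigraphy summary per patient per titration dose, with dose as an ordinal term. State whether the baseline and fixed-dose weeks enter, and reconcile the seven-day blocks in 7.1 with the continuous collection in 7.2, 7.6 and 7.8. State also that dose is confounded with study week, and that patients who reach higher doses are selected for tolerance; the model removes neither problem.

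Cost: two short paragraphs and slightly more analysis work in standard software. All the data are already collected.
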